Results are better in paroxysmal patients, than for persistent AF, also for CBA. [13] Nevertheless, persistent patients with normal left atrial dimensions made up an important proportion of our group. [15] Differentiation between paroxysmal and short term persistent becomes almost impossible from a clinical point of view, as patients get early cardioversion, before they are spontaneously reverted to sinus rhythm. [16] Real longstanding persistent patients, however were excluded from our and all previous trials, as were patients with very large atria. Larger atria have more recurrences than smaller atria. Successful ablation results in a smaller left atrial volume, which was shown in several studies with RF, also for paroxysmal patients. [17] This volume reduction is antiarrhythmic as well.

It has been hypothesized that early therapy prevents further progression of the disease. [16] This has never been proven for catheter ablation, while some pilot trials were promising. [18] Reduction of left atrial volume can be used as a substitute for antiarrhythmic efficacy and for less disease progression.

RATIONALE

Limited data indicate that ablation is better than AAD therapy. The 9 small randomized clinical trials as recently summarized by health care authorities with a correct methodology only included 971 patients, and only studied radiofrequency ablation. [19] However, there was substantial heterogeneity, with a majority of paroxysmal patients, but some had mixed groups. Endpoints in these trials were not always clear and variable as well. Side effects of ablation were somewhat neglected. Stop-AF only addressed paroxysmal patients (but included 22% cardioverted patients) and has recently been published. [14] This opens the perspective to organize a prospective trial comparing the efficacy and safety of CBA to standardized medication for treatment of paroxysmal AF and early onset persistent AF without structural heart disease. As elsewhere a trial is launched for first onset paroxysmal AF, we would like to focus in this protocol *on early onset persistent AF without structural heart disease*. The value of CBA in these patients has never been studied; the endpoints for persistent patients are much easier than for paroxysmal patients. Reduction in LA size can be compared versus patients on drug therapy and versus failing patients.

HYPOTHESIS

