1. The results of CBA in early onset persistent AF are better compared to standard medical therapy with as endpoint maintenance of sinus rhythm after 1 year and an improved QOL in the ablation group.
2. Successful CBA results in reduction of the LA volume.

INCLUSION/EXCLUSION CRITERIA

The total AF history is regarded for previous episodes, paroxysmal or persistent. ~~should be shorter than 24 months~~. Symptomatic patients can be included if they have had at

least 2 episodes in their total history, of which one within the last year. One episode in the entire history should have lasted more than 7 days **48 h**, requiring electrical or pharmacological cardioversion or stopped spontaneously after more than 7 days. The duration of this episode should be shorter than 1 year. If one episode is paroxysmal it should have been lasting minimal 30 sec.

All patients eligible for the study will sign informed consent, have an echocardiogram prior to inclusion to exclude severe left ventricular dysfunction, to rule out significant valve abnormalities, left ventricular hypertrophy and to assess the left atrial (LA) volume and diameter.

Prior to randomization, and after inclusion it is suggested to the local investigators to perform an MRI-scan or CT scan of the LA and pulmonary veins (in both branches of the study) in eligible patients to assess the anatomy and the left atrial volume. The results should not influence the strategy of treatment.

Inclusion criteria

- > 21 years and legally capable
- history of 2 symptomatic AF episodes more than 30 sec .
- At least one AF episode within the last year
- One episode cardioverted after more than 7 days or spontaneously terminated after more than 7 days; this episode should have been shorter than one year
- Eligible for at least one first step drug therapy (sotalol, propafenone, or flecainide) **and/or** for amiodarone

- Left ventricular ejection fraction estimated > 45%
- LA diameter < 50 mm (parasternal short axis) **and/or** LA volume less than 100 ml (apical view, Area Length method)
- No previous CVA or TIA (the latter with documented deficit on CT scan)
- ~~CHADS2VASC ≤ XXXX~~
- Failed AAD strategy, or untreated with AAD
- No use of Amiodarone in the previous 6 weeks (except IV or oral for 7 days)
- Informed consent

Exclusion criteria

- Age **> = 80** yrs
- CHF
- Ischemic heart disease as known in the history
- (Severe) Left ventricular hypertrophy as shown on echo (IVSd or PWd > 14 mm)

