- Uncontrolled Hyperthyroidism
- Congenital heart disease
- HCM, ARVC, channelopathies
- Contra-indications to AAD
- Long QT syndrome

- Received already adequately dosed all level 1 drugs (sotalol, propafenone, and flecainide) and >6 weeks amiodarone
- Pure (typical) atrial flutter as documented on one occasion

INVESTIGATION DESIGN

Type

Randomized study design. Experienced centres/operators with a load of > 50 cryoablations/year.

Randomization

1:1 at the time of inclusion

SAMPLE SIZE

The maximal expected 1 year success on AAD is 50% and minimal expected success of CBA is 72%. [3,14,15,20,21,22] With a power of 0.8 and a significance of 0,05, approximately 76 patients should be included in each arm. A total number of 167 patients need to be included in the study when anticipating that 10% of the patients will not be followed as required.

INTERVENTIONS

Run-in period (from month -1 till month 0)

Holter recording in the month after inclusion, preferably directly after inclusion to avoid extra visits.

MRI or CT scan to measure LA volume and PV sizes and anatomy is encouraged

(optional – if done it should be done in both branches)

Ablation arm (at month 0):

The ablation approach should be as standardised as possible, and will be discussed at the investigators meeting

After venous punctures, 5000 IE of heparin is administered and after the transseptal puncture (TSP) this is repeated. Hereafter, heparin infusion is started with a target ACT of at least 275-300 s. A multipolar catheter will be introduced into the coronary sinus. Single TSP will be performed (guided by X-ray and intracardiac echocardiography or transoesophageal echocardiography). The 12 Fr steerable sheath is introduced into the LA, and the second generation (large) cryoballoon with the Achieve catheter is introduced. Before ablation is started, the veins are checked for entrance and exit block. If there is conduction a balloon application is given during 300 s. The occlusion grade, maximal freezing temperature and time to isolation are noted. Every vein with potentials is ablated at least twice with at least one grade IV occlusion, except when PNP occurs at the right upper PV. If not isolated, a third application can be given. If after the third application the vein is still not occluded it is up to the physician to decide to do another balloon application or to use a freezer catheter.

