If isolated, the veins are checked after 30 minutes again for entrance and exit block. The left sided veins are ablated while pacing from the distal CS electrodes and when ablating the right sided veins the phrenic nerve is stimulated to prevent phrenic nerve palsy (PNP). When all veins are isolated AF induction is preformed, 5 s of pacing with CL 200 ms from the distal CS, LA roof (twice) en the HRA. Procedure times , X-ray times, and the radiation dose (mGy) are noted.

Ablation should be scheduled 4 weeks after cardioversion/inclusion. All patients should

be anticoagulated for at least 4 weeks prior to ablation. Antiarrhythmic drugs are maintained after cardioversion. One day before or the day of ablation a TEE will be made to exclude a LAA thrombus. Anticoagulation can be continued if this is the protocol of the participating centre, and the local protocol per ablation should be followed.

Proposed first level:

A: propafenone 300 mg BID / 150 mg QID if < 70 years and > 70 kg

propafenone 150 mg TID if ≥ 70 years or < 70 kg

B: sotalol 120 mg BID if men ≤ 70 years, cr ≤ 1,5mg/130 µmol, > 70kg;

80 mg TID if men ≥ 70 years, cr > 1,5mg/130 µmol, < 70kg;

if women ≤ 70 years; cr ≤ 1,2/110 µmol

80 mg once if women > 70 years or cr > 1,2 mg/110 µmol

C: Flecainide : Apocard Retard 100 mg/day as startdosis 4 to 5 days

Further 200 mg/day

Tambocor 100 mg BID if preferred

Proposed second level:

Amiodarone: loading 14 days with 600 mg/day

One week 400 mg/day

Maintenance 200 mg/day

Drug arm:

Anticoagulation should be continued per protocol (4 weeks) after the cardioversion. If the CHADS2VASC is \leq 2, anticoagulation is left at the discretion of the physician. A first level antiarrhythmic drug regimen is started at the month -1, time of the inclusion and

an adequate dosage is prescribed. If the patients' condition requires so, a reduced dosage can be used during the first (5-7) days.

If at month 0, at the first clinical visit, the drug therapy does not look sufficient, another

Level 1 treatment can be used. This can be repeated if the clinical condition requests so.

The second slevel antiarrhythmic drug therapy is only allowed after failure of at least one level 1 drug. As this is amiodarone, its final efficacy can only be judged 6 months after its initiation.

FOLLOW UP : see flow charts Is in agreement with proposal in ref 23.

- 24 hour Holter:

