 - after inclusion (month -1) and repeated at months 3 .This will be done with the study Holter without necessarily influencing the therapy (so called blanking period)
- 48 hour Holter: with a clinical device
 - at the end of 6 months .
- 7 days Holter: with a clinical device
 - at the end of 12 months .
- Clinical visits :

should be performed by the study nurses/supervised by the investigators

- At months 3, 6, and 12 months after ablation
- Additionally at month 0 for the drug arm, while the ablation group is admitted
- Office ECG ;
 - ° at month 3, 6 and 12
- Drug management:
 - AAD: After 3 months stop AAD in the ablation arm in those patients free of AF episodes.
 - OAC: After 6 months consider stopping oral anticoagulation, or replacing them with antithrombotic medication in patients free of AF episodes if the scores allow so.
- Echocardiogram:
 - At month 12 a new echocardiogram is obtained to assess the LA volume and diameter.
- QOL with disease specific questionnaire (AFQOL 18)
 - At baseline and at month 12
- Blood samples
 - At baseline and at months 6 and 12
 - Thyroid tests (TSH), liver function (AP, SGOT, SGPT), creatinine

- Drug diary
 - At baseline, at month 0 and at months 6 and 12 for all patients in both arms
- Cost calculation: data should be prospectively collected in CRF at the time of scheduled and unscheduled visits, based on costs as foreseen in the reimbursement of the RIZIV/INAMI and additional drug costs.

CROSS OVER

Is allowed after 6 months. This implies that at 12 months we will be able to do not only ITT but also OTA.

SERIOUS ADVERSE EVENTS

SAE's are expected to happen in 7% in the ablation arm, and at a rate of 12-15% in the drug arm, because of side effects and 3% because of proarrhythmia (20).

ENDPOINTS

Primary endpoints

- Sinus rhythm at clinical visit at 1 year after the ablation, or with AAD
- Freedom of AF with all measurements

Secondary endpoints

- Reduction of LA volume in successfully treated patients
- Number of cardioversions
- Percentage of patients on AAD after 6 and 12 months

- Vascular complications
- Stroke, TIA
- SAE in both groups
- Number of cross-overs (with OTA)

[figure not shown]

Figure 1. AAD : antiarrhythmic drugs; LA: left atrial; QOL: quality of life; R: randomization

STUDY ORGANISATION

Steering committee : [name], [name], [name], [name]

DMSB : [name], [name], [name]

One central study coordinator (University Hospital Ghent) – [name]

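### Rhythm at the baseline LA volume scan is left open while month 12 scans in successes are mostly in sinus rhythm by selection, so part of the reported reduction may not be remodelling after ablation

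*Protocol*

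**What the plan says.** - **Role of the measure.** Protocol, Background: "Reduction of left atrial volume can be used as a substitute for antiarrhythmic efficacy and for less disease progression". Protocol, Hypothesis, item 2: "Successful CBA results in reduction of the LA volume". No comparator is named there. The Rationale adds that the change in LA size can be set against drug-treated patients and against failing patients.
- **Endpoint.** Protocol, Endpoints, secondary: "Reduction of LA volume in successfully treated patients". The first primary endpoint is "Sinus rhythm at clinical visit at 1 year after the ablation, or with AAD"; the second is freedom from AF on all measurements.
- **Baseline scan.** Protocol, Inclusion/Exclusion Criteria: patients "have an echocardiogram prior to inclusion to exclude severe left ventricular dysfunction", and the same scan gives LA volume and diameter. The inclusion limit for volume uses the apical area-length method.
- **Follow-up scan.** Protocol, Follow Up: "At month 12 a new echocardiogram is obtained to assess the LA volume and diameter".
- **Timing against cardioversion.** Protocol, Interventions, Ablation arm: "Ablation should be scheduled 4 weeks after cardioversion/inclusion". The drug-arm text also refers to anticoagulation for a period after cardioversion.
- **Entry rhythm.** The inclusion criteria ask for an AF episode within the last year and for one long episode that was cardioverted or ended by itself. They do not ask for AF at inclusion.
- **Other imaging.** Protocol, Run-in period: "MRI or CT scan to measure LA volume and PV sizes and anatomy is encouraged". It is optional, and the visible schedule shows no repeat.

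None of these places sets the rhythm at the echo, the interval from cardioversion, or an adjustment for either. The flow charts and the SAP text were not available for this check, so a rule there cannot be excluded.

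**The concern.** The endpoint is a before-after change in a group chosen by its outcome. Success under either primary definition means that the month 12 scan is mostly taken in sinus rhythm. Nothing similar applies to the baseline scan. If measured LA volume depends on rhythm, the two ends of the change are not measured under the same condition. If volume reads larger in AF, the imbalance in successes can only act towards an apparent reduction.

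There is a second route. The baseline scan precedes inclusion, and ablation follows about four weeks after inclusion or cardioversion. Any recovery after cardioversion in that interval is counted as change after ablation.

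At stake is Hypothesis 2. It could be confirmed without any remodelling due to cryoballoon ablation, and the protocol gives this measure weight as a stand-in for efficacy and for disease progression. The contrast with failing patients is exposed in the same direction, because failures are more likely than successes to be in AF at month 12.

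**Working it through.** **Plan's own figure.** The plan states no number for LA volume. The only sample size is for the primary success comparison: 50% against 72%, alpha 0.05, power 0.80. The two-sided pooled formula without continuity correction gives 76 per arm, as stated. It is used here only to get the expected number of ablation successes: 76 x 0.72 = 54.7, about 55.

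**Change in successes.** Let p be the share of successes scanned in AF at baseline and d the ml that AF adds to measured volume. Take all successes to be in sinus rhythm at month 12, with no true remodelling.

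- Apparent mean reduction = p x d.
- The documents give neither p nor d. Assumed: p = 0.3 to 0.7; d = 4 to 12 ml (5% to 15% of an assumed 80 ml atrium).
- Low end: 0.3 x 4 = 1.2 ml. High end: 0.7 x 12 = 8.4 ml. Middle: 0.5 x 8 = 4 ml.
- If p = 0 or d = 0, the artefact is 0.

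This covers only rhythm at the scan. Recovery after cardioversion would add to it and cannot be sized from the documents.

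**Chance of a false confirmation.** For a paired test in 55 successes with artefact a = p x d, SE = SD/√55 and

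P(two-sided p < 0.05) = 1 − Φ(1.96 − a/SE) + Φ(−1.96 − a/SE).

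The SD of change is also assumed. SD 15 ml gives SE 2.02; SD 10 ml gives SE 1.35. A second, somewhat lower set of assumed p and d is used here.

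| p | d (ml) | a (ml) | SD 15 ml | SD 10 ml |
|---|---|---|---|---|
| 0 | any | 0 | 5% | 5% |
| 0.2 | 3 | 0.6 | 6% | 7% |
| 0.4 | 5 | 2.0 | 17% | 32% |
| 0.6 | 10 | 6.0 | 84% | 99% |

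The result runs from the nominal level to near certainty. The table shows that the artefact could matter, not that it does.

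**Contrast with failing patients.** Let q be the share of failures in AF at the month 12 scan, with the same p at baseline in both groups. The rhythm-driven mean change is −p x d in successes and (q − p) x d in failures, so the spurious difference is q x d whatever p is. If all failures are in AF (q = 1), it is the full d; if half are, it is d/2.

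**The case against.** **AF at baseline is not documented.** A reader might infer that many patients are in AF or just cardioverted at the baseline echo, so that a rhythm effect is certain. The documents do not support that. The last episode may be up to a year old, the qualifying long episode is described as already ended, and the phrase joining cardioversion and inclusion can be read as whichever applies. This stands: the text supports that some patients may be affected, not how many.

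**The size comes from assumptions.** No passage says that LA volume reads larger in AF, and p, d and the SD are all assumed. This also stands, and it limits the conclusion to an artefact of unknown size.

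**A between-arm bias of 1 to 3 ml.** A reader might multiply the difference in expected success by d: (0.72 − 0.50) x 4 to 12 ml = 0.9 to 2.6 ml. That needs every non-success to be in AF at the month 12 echo. Under the freedom-from-AF definition, a patient with AF on an earlier recording is a failure yet may be in sinus rhythm at the scan. Cross-over after 6 months may narrow the gap further. The figure is nearer an upper bound. Randomisation also balances baseline rhythm between arms, and month 12 rhythm is partly a consequence of treatment.

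**Rhythm is recorded elsewhere.** Office ECG and 7-day Holter are scheduled at month 12, a 24-hour Holter follows inclusion, and cardioversions are counted. Month 12 rhythm is thus largely captured. What remains open is rhythm, and time since cardioversion, at the scan before inclusion.

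**A smaller atrium under sinus rhythm is a real effect.** Hypothesis 2 does not claim remodelling independent of rhythm, and for a marker of antiarrhythmic efficacy such a reduction is partly intended signal. This is fair, but it does not cover a difference in measuring conditions, or a recovery that happened before the ablation.

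**MRI/CT.** A reader might suspect that a baseline MRI/CT volume will be paired with a month 12 echo. No passage proposes this.

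**Conclusion.** The concern holds in a limited form. As visible, the plan cannot separate remodelling after ablation from rhythm at the scan or recovery after cardioversion, because baseline rhythm is open and month 12 rhythm in successes is largely fixed by selection. The artefact is p x d: about 1 to 8 ml under the assumed ranges, and zero if no success was scanned in AF at baseline. Without baseline rhythm on record, its size could not be checked afterwards.

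The documents do not show that such an artefact is present, nor that a comparison of arms as randomised is biased by a known amount. The reach is Hypothesis 2, one secondary endpoint, and the comparison with failing patients mentioned in the Rationale. The primary endpoints and the sample size are untouched. The conclusion would change if the SAP, the CRF or the flow charts already fix or record rhythm at the baseline echo; the sponsor need then only point to the rule.

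**What to change.** - Record at each echo the rhythm during the scan and the date of the last cardioversion.
- Define LA volume change as echo to echo, by the area-length method already used for inclusion, and adjust or stratify it by rhythm at the baseline scan.
- For any comparison between arms, analyse all pairs by randomised arm first. Adjusting for baseline rhythm does not remove differences in month 12 rhythm, so describe month 12 rhythm by arm beside the result.
- Report pairs in sinus rhythm at both scans as a supportive analysis. It should not be the main result, because it conditions on a state that arises after randomisation.

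The cost is one CRF item (rhythm with cardioversion date) and some analysis wording, with no extra scan and no change in sample size. The supportive analysis will have fewer pairs, and the reported reduction may be smaller.

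### Quality of life has no post-baseline measurement before cross-over opens, so its only between-arm comparison, at month 12, may be diluted with no earlier value beside it

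*Protocol*

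**What the plan says.** - **Hypothesis, item 1** couples two outcomes: "maintenance of sinus rhythm after 1 year and an improved QOL in the ablation group".
- **Follow up** names the instrument, "QOL with disease specific questionnaire (AFQOL 18"), and its times: "At baseline and at month 12". Clinical visits take place "At months 3, 6, and 12 months after ablation". At month 6 the protocol already schedules a visit, an ECG, a 48-hour Holter, blood samples and a drug diary. It does not schedule QOL.
- **Cross over**: "Is allowed after 6 months. This implies that at 12 months we will be able to do not only ITT but also OTA". The section gives no criteria, direction or expected rate.
- **Endpoints**: QOL is in neither the primary nor the secondary list. The secondary list does include "Number of cross-overs (with OTA").
- **Sample size** concerns 1-year success only: 50% on drugs, 72% on cryoballoon ablation, about 76 patients per arm and 167 in total.

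**The concern.** One half of Hypothesis 1 rests on a single post-baseline measurement, taken six months after patients may begin to change treatment. The drug-arm patients most likely to want ablation are plausibly those whose drugs have failed, and they carry much of any QOL contrast. If they are ablated and improve before month 12, the drug-arm average rises and the ITT difference shrinks. Regrouping patients by treatment received does not repair this, because the regrouping follows a choice made after randomisation. For rhythm, the Holter and ECG data at months 3 and 6 show how the arms compared before cross-over. For QOL there is nothing to look back on, and a questionnaire not completed at the time cannot be recovered later.

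**Working it through.** **Plan's own figure.** With 50% and 72%, two-sided 0.05, power 0.80 and pooled variance (mean proportion 0.61):

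n = [1.96·√(2·0.61·0.39) + 0.842·√(0.50·0.50 + 0.72·0.28)]² / 0.22² ≈ 76 per arm.

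The total is 2·76·1.10 = 167.2, which matches 167. The protocol does not state sidedness; the two-sided version reproduces its figure. The calculation covers rhythm only and says nothing about power for QOL.

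**Timing.** The only post-baseline QOL value is at month 12 and cross-over opens after month 6, a gap of 12 − 6 = 6 months. The number of post-randomisation QOL assessments before cross-over opens is 0. The protocol does not say from when the 6 months run. Counted from inclusion (month −1), the gap would be about 7 months, with the same conclusion.

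**Illustration of dilution.** The documents give no QOL effect, standard deviation or cross-over rate, so this shows mechanism and range. It is not a forecast. Assumptions:

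1. QOL gain follows rhythm success: 1 for success, 0 for failure. The arm means without cross-over are then 0.72 (ablation) and 0.50 (drug), a difference of 0.22.
2. A share c of the whole drug arm crosses over, and all who cross are drug failures (score 0).
3. By month 12 those crossing reach a fraction r of the ablation-arm mean.

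Drug-arm ITT mean = 0.50 + c·r·0.72. Share of the difference lost = c·r·0.72 / 0.22.

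| c | r | Drug-arm mean | Remaining difference | Cut |
|---|---|---|---|---|
| 10% | 1 | 0.572 | 0.148 | 33% |
| 10% | 0.5 | 0.536 | 0.184 | 16% |
| 25% | 1 | 0.680 | 0.040 | 82% |
| 25% | 0.5 | 0.590 | 0.130 | 41% |

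If those crossing were instead typical of the drug arm and reached 0.72, the difference would be (1 − c)·0.22, a cut of 10% or 25%. Who crosses therefore matters as much as how many.

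**The case against.** **The month-12 ITT analysis is valid.** This stands. It compares early ablation with drugs first and cross-over allowed after 6 months, and Hypothesis 1 is framed at 1 year. If drug-arm patients cross and benefit, it errs toward no difference and does not create a false positive. A reader might infer that the plan has no randomised QOL comparison at all. The documents do not support that: what is missing is one free of cross-over.

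**Month 6 is not neutral.** This also stands. Under Interventions, Drug arm, amiodarone may follow only after at least one first-level drug has failed, and the protocol says its final efficacy can be judged only 6 months after it is started. First-level drugs start at month −1 and are first reviewed at month 0. A patient moved to amiodarone after month 0 therefore has less than 6 months on it at the month-6 visit, and the comparison there could lean toward ablation. It may be tempting to make month 6 the test of the QOL hypothesis. The protocol's own statement on amiodarone argues against that.

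**The size is unknown.** Correct. Full recovery by month 12 is a strong assumption. The protocol asks for at least 4 weeks of anticoagulation before ablation and describes the early Holters, up to month 3, as a blanking period, so late crossers could recover only in part. A reader might also want a figure for lost QOL power. None can be derived, because the protocol states neither a QOL effect nor a QOL power to lose.

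**QOL is not a listed endpoint, and other outcomes share the problem.** Both are true. The 1-year rhythm endpoint and month-12 left atrial volume are also measured after cross-over opens. The missing endpoint listing lowers the weight of the point, but the QOL claim still stands in Hypothesis 1. Rhythm, unlike QOL, has interim data.

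The flow charts and the SAP text were not available for this review, so the finding rests on the protocol's written schedule, which is explicit.

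**Conclusion.** The point holds as a gap in measurement timing. The protocol plans no QOL value between randomisation and the opening of cross-over. The month-12 ITT comparison remains the proper 1-year randomised test of strategies, but it may understate the QOL effect of the treatments as assigned, and nothing collected earlier would show by how much.

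The size cannot be determined from the documents. With QOL tracking rhythm success and only failures crossing, 10% crossing costs about 33% of the difference and 25% about 82% under full recovery. With half recovery the figures are about 16% and 41%. If cross-over turns out to be rare, or those who cross gain little, the dilution is small.

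**What to change.** Add AFQOL 18 at the existing month-6 visit in both arms, completed before any cross-over decision. State from when the 6 months in the Cross over section are counted: if they run from inclusion (month −1), cross-over could open before the month-6 visit, and the questionnaire must still come first.

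Report the month-6 difference by assigned arm, adjusted for baseline, as a supportive cross-over-free analysis. Keep the month-12 ITT result as the 1-year test and show the two side by side with the number of cross-overs.

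The cost is one questionnaire at a visit already planned, a small patient burden and one further analysis. The limitations to state with the result are the shorter follow-up and the possible tilt toward ablation, because drug-arm patients moved to amiodarone after month 0 cannot, on the protocol's own terms, be finally judged at month 6. Reporting how many patients this concerns would let readers weigh it.

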PROSPECTIVE STUDY OF MEDICAL THERAPY AGAINST CRYOBALLOON ABLATION IN PATIENTS WITH SYMPTOMATIC RECENT ONSET PERSISTENT ATRIAL FIBRILLATION:
METACSA

[name], [name], [name], TBD, [name] and [name]

BACKGROUND

Atrial fibrillation (AF) is the most common cardiac arrhythmia and causes significant morbidity and mortality. AF is not benign, as the mortality risk is doubled and the risk for stroke, left ventricular dysfunction and hospitalization are increased. The prevalence is 1-2%, and increases with age. [1] The health care burden is substantial. [2]

Treatment of AF is targeted on prevention of thrombo-embolic complications and the reduction of symptoms. Medication includes anticoagulation and anti-arrhythmic drugs (AAD) for either rhythm or rate-control. Although AAD are the first line of therapy, they have their shortcomings, as most AAD have been shown only to be 40-50% effective in maintaining sinus rhythm and may have serious side effects. Only amiodarone performs better, but its side effects are substantial, and it is withdrawn of treatment in about 20% of patients, which makes its efficacy comparable to that of propafenone. [3,4]

Ablation of the pulmonary veins (pulmonary vein isolation, further PVI) has proven to be a safe and effective treatment for AF with variable success rate, depending on the AF type, and the presence or absence of underlying disease. [5,6] Recent data show that non-repeated PVI with radiofrequency (RF) ablation, has only a limited effect at one year (50-60%). These results can be improved with a repeated ablation, and seem not

be maintained after 5 year. [7-11] These are some of the arguments that alternative techniques are still being investigated, inclusive minimal invasive surgical techniques.

Success rates, at least similar to RF ablation have been reported after 1-year follow-up and later with a freedom from AF of 69-77% in patients using a cryoballoon technology (CBA). [12-14]. CBA seems to be a reproducible technique, with the same outcome in different centers. It has theoretically less side effects than RF, and its only specific side effect is phrenic nerve paresis.

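### The 76 per arm allows nothing for cross-over from month 6, and the readable text gives no rule for scoring crossed-over patients on the 1-year sinus rhythm primary endpoint

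*Protocol*

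**What the plan says.** - **Sample size (Protocol, SAMPLE SIZE).** The planning rates are: "The maximal expected 1 year success on AAD is 50% and minimal expected success of CBA is 72" per cent. With power 0.8 and significance 0.05 this gives about 76 per arm. The total of 167 comes from "anticipating that 10% of the patients will not be followed as required". No other inflation is mentioned.
- **Cross-over (Protocol, CROSS OVER).** "Is allowed after 6 months. This implies that at 12 months we will be able to do not only ITT but also OTA". No direction, trigger, expected rate or scoring rule follows, and OTA is not defined. The number of cross-overs is a secondary endpoint, so some are expected.
- **Primary endpoints (Protocol, ENDPOINTS).** There are two: "Sinus rhythm at clinical visit at 1 year after the ablation, or with AAD" and "Freedom of AF with all measurements". The text does not say which was sized or which decides the trial.
- **Where the rates seem to come from.** BACKGROUND reports cryoballoon results "with a freedom from AF of 69-77% in patients using a cryoballoon technology" and says "most AAD have been shown only to be 40-50% effective in maintaining sinus rhythm". HYPOTHESIS 1 refers to "endpoint maintenance of sinus rhythm after 1 year and an improved QOL in the ablation group". This language describes sustained freedom from AF rather than the rhythm at one visit.
- **Monitoring (Protocol, FOLLOW UP).** An ECG and a 48-hour Holter are already scheduled at month 6, with no distinction between arms. The month-3 Holter is placed in a blanking period.

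**The concern.** Cross-over opens halfway to the assessment of the sinus rhythm endpoint. Take a drug-arm patient who relapses, is ablated at month 7 and is in sinus rhythm at month 12. Under plain ITT on that endpoint, this patient is a drug-arm success. Each such patient pulls the drug arm towards the ablation arm, and the sample size has no margin for it.

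The Protocol's answer is that OTA will also be possible. If that means analysis by treatment received, drug failures leave the drug group and raise its success rate. Patients ablated less than 6 months earlier join a group whose endpoint is set at 1 year, and the randomised comparison is lost.

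The freedom-from-AF endpoint behaves differently, because AF recorded before cross-over stays a failure. The two primary endpoints could therefore disagree because of the same cross-overs, with nothing in the readable text to say which prevails.

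**Working it through.** **1. The plan's own figure.** Two-sided 5% test of two proportions, pooled variance, p1 = 0.50, p2 = 0.72, mean 0.61:

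n = [1.96·√(2·0.61·0.39) + 0.8416·√(0.50·0.50 + 0.72·0.28)]² / 0.22² = (1.352 + 0.566)² / 0.0484 ≈ 76.

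Power at 76 per arm is 0.800. The total is 2 × 76 × 1.10 = 167.2, the stated 167. The 10% is used up by patients not followed. If nobody were lost (about 83 per arm), power would be 84%, a small cushion.

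**2. ITT on 1-year sinus rhythm.** Assumptions, none of them given in the documents:
- k = number of the 76 drug-arm patients who cross over (illustrative)
- s = share of them in sinus rhythm at month 12 after ablation, 50% to 72% (the two planning rates)
- q = share who would have been in sinus rhythm at month 12 had they stayed on drug

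Drug-arm success = 0.50 + (k/76)(s − q). Example with k = 8, s = 0.72, q = 0: 0.50 + (8/76)(0.72) = 0.576 against 0.72, power 46%.

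Power at 76 per arm, k = 8 (pairs are s = 50% / s = 72%):

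| q | Drug-arm success | Power |
|---|---|---|
| 0% | 0.553 / 0.576 | 57% / 46% |
| 25% | 0.526 / 0.550 | 70% / 59% |
| 50% | 0.500 / 0.523 | 80% / 71% |
| 100% | 0.447 / 0.471 | 93% / 89% |

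The effect can go either way: dilution when q < s, and a shift in favour of ablation when q > s. At the extreme q = 0, power is 70-64% for k = 4 and 45-28% for k = 12.

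**3. Less conservative rates.** Assume 45% versus 75%, inside the BACKGROUND ranges of 40-50% and 69-77%. With q = 0, drug-arm success = 0.45 + (k/76)s. Power is 97% at k = 0, 89-83% at k = 8 and 82-68% at k = 12.

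**4. OTA read as treatment received, q = 0, planning rates.** Drug group = 38/(76 − k). Ablation group = (54.72 + s·k)/(76 + k). For k = 8: 38/68 = 0.559 against 0.699 / 0.720, power 43% / 54%. For k = 4, 64% / 69%; for k = 12, 23% / 37%.

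**5. Freedom from AF by ITT, same cross-overs.** Let u be the share of failing cross-overs with no AF recorded beforehand. Drug-arm success = 0.50 + u·s·k/76.

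| u | Power, k = 8 | Power, k = 12 |
|---|---|---|
| 0% | 80% | 80% |
| 25% | 75% / 73% | 72% / 69% |
| 50% | 70% / 64% | 64% / 55% |

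Steps 2 and 5 put the same 50% and 72% on two different endpoints. That is a convenience for comparison; the documents do not give separate rates.

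**The case against.** Several counter-arguments have weight.

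- **The planning rates are a floor.** The Protocol calls 50% maximal and 72% minimal. Step 3 shows that modestly better rates absorb 8 cross-overs. This stands. A reader might infer that the trial is underpowered, or that neither ITT nor OTA can keep 80% power; the documents do not support that. It follows only at the planning rates, with cross-overs who would mostly have failed on drug, and with OTA taken as as-treated.
- **q = 0 is the extreme.** A patient with recurrences can be in sinus rhythm at one visit, cardioversions are expected, and some patients will change treatment for side effects. This also stands, so the range over q belongs beside the lowest figures.
- **The endpoint wording may already exclude cross-overs.** A drug-arm patient ablated at month 7 is neither 1 year after ablation nor necessarily on a drug. Scoring such patients as failures would restore 50% versus 72% and 80% power. The reading is possible, but no rule states it.
- **The rates may belong to freedom from AF.** If so, no power was ever stated for single-visit sinus rhythm, and the sized endpoint is largely protected. That is probably the better reading, and it supports the fix. The text does not say so, however, and both endpoints are primary.
- **OTA is undefined.** An on-treatment analysis that takes status at the switch would keep drug failures as failures. Again, nothing says this is meant.
- **The rule may be elsewhere.** The SAP text, part of the Protocol, the flow charts and Figure 1 could not be read, and could settle the scoring.

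**Conclusion.** The point holds in a limited form. The sample size contains no cross-over allowance, and on the readable text a plain ITT reading of 1-year sinus rhythm can count an ablated drug failure as a drug success.

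The size depends on inputs the documents do not give. With 8 of 76 crossing over at the planning rates, power ranges from 46% to 80% as q goes from 0 to 50%. It exceeds 80% if most cross-overs would have been in sinus rhythm on drug, or if the true rates are about 45% versus 75%. An as-treated OTA offers no rescue when the cross-overs are drug failures. Freedom from AF by ITT keeps 80% when AF was recorded before cross-over.

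This is an inexpensive clarification worth making, not a demonstration that the trial fails. Confidence is medium because of the unreadable material.

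**What to change.** 1. **SAMPLE SIZE and ENDPOINTS:** state that 50% versus 72% and 76 per arm refer to freedom from AF on all measurements, analysed by ITT, and that this endpoint decides the trial.
2. **CROSS OVER:** add that the scheduled month-6 ECG and 48-hour Holter are completed before any change of treatment; that AF recorded after month 3 and before cross-over remains a failure whatever the later rhythm; and that patients who cross over without recorded AF stay in their randomised arm.
3. **1-year sinus rhythm:** report it as supportive, with a sensitivity analysis that scores drug-arm patients who crossed over for AF as failures.
4. **OTA:** define it and label it exploratory.

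**Cost.** A few sentences of text; no extra patients or tests. Cross-over remains available from month 6, so a larger sample or a later cross-over is not needed. Nor is an extra ECG for cross-overs only, which would add AF detection mainly in one arm. The price is that 1-year sinus rhythm loses its primary status. AF never recorded before cross-over can still shift the result, by the amounts in step 5 of the working.
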